9.4.1.2. Sensitivity Analyses of the Primary Efficacy Endpoint

To further evaluate and demonstrate the robustness of the results for the primary efficacy outcome, the following supportive sensitivity analyses will be conducted.

9.4.1.2.1. Odds ratio from a logistic regression model

A logistic regression with treatment as the main effect (using placebo as the reference category) will be used for comparing the primary efficacy endpoint between the treatment groups. The odds ratio and corresponding 2-sided 95% Wald confidence interval will be provided.

The analyses above will be performed based on the ITT population.

9.4.1.2.2. Analysis in other analysis populations

Fisher's exact test for the primary efficacy endpoint will be performed on the mITT and PP populations as defined in Sections 7.3 and 7.4, respectively. The estimated responder rates and the corresponding exact 95% confidence interval based on binomial distribution will be calculated for each treatment group. The exact 95% confidence interval of the responder rate difference will also be obtained.

9.4.2. Subgroup Analyses of the Primary Efficacy Endpoint

For each subgrouping variable identified in Section 7.5 meeting the minimum group size requirement (the subgroup is included if there are $\geq 10\%$ of subjects within that subgroup), the available data for primary efficacy endpoint will be summarized by treatment group for the ITT population. Fisher's exact test will be performed within each such subgroup.

The Cochran–Mantel–Haenszel test will be performed to compare the responder rates between the treatment groups adjusted for the subgrouping variable. Additionally, the possible treatment-by-subgroup interaction will be tested for each subgrouping variable as follows:

- The Breslow-Day test will be performed for each subgrouping variables. If the p-value of the Breslow-Day test is ≥ 0.05, the treatment-by-subgroup interaction is not significant.
- If the interaction effect is statistically significant (i.e., p-value < 0.05), then the Gail and Simon¹ test will be used to test for the qualitative interaction at a significance level of 0.05 and provided as an aid for interpretation.

9.4.3. Analysis of Covariates

The logistic regression model with treatment and all covariates listed in Section 4.5 will be used to obtain the 2-sided 95% confidence intervals for the covariate-adjusted estimate of the treatment effect for the primary efficacy endpoint.

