1. INTRODUCTION

This document outlines the statistical methods to be implemented during the analyses of data collected within the scope of Helixmith Co., Ltd. (formerly ViroMed Co., Ltd.) Protocol VMNHU-003/I [A Phase III, Double-Blind, Randomized, Placebo-Controlled, Multicenter Study to Assess the Safety and Efficacy of VM202 to Treat Chronic Nonhealing Foot Ulcers in Diabetic Patients with Concomitant Peripheral Arterial Disease (PAD)]. The purpose of this plan is to provide specific guidelines from which the analysis will proceed. Any deviations from these guidelines will be documented in the clinical study report.

Study enrollment commenced under Protocol VMNHU-003/C. There were 7 subjects enrolled under protocol version C, 5 enrolled under version E, 16 enrolled under version F, and 16 enrolled under version G; no subjects were enrolled under protocol version D, H or I.

Protocol VMNHU-003/E introduced the following changes to exclusion criteria in VMNHU-003/C:

- The study ulcer decreased by 50% or more at baseline from Screening (as assessed by comparison of post-debridement photos taken at Screening and Day 0); previously only ulcers that increased by 50% or more at baseline from Screening were excluded.
- Target ulcer located on an active (hot) Charcot foot; previously any Charcot foot was excluded.
- Body mass index (BMI) > 45 kg/m² at Screening; previously BMI > 35 kg/m² was excluded.
- All steroids except inhaled or ocular steroids; previously only high dose steroids were excluded.

Since these changes to the exclusion criteria were not expected to have a meaningful influence in favor of VM202 on the efficacy and safety parameters, no inferential analyses to account for the protocol version will be conducted. Descriptive summaries of the primary efficacy endpoint and overall adverse event rates will be produced for the subjects enrolled under different versions of the protocol.

Protocol VMNHU-003/F submitted with SAP revision C introduced the following changes to the inclusion criteria:

- the upper age limit for study participants will be raised to 80 years;
- addition of ABI > 1.4 (indicative of non-compressible vessels at the ankle) as a qualifying criterion for documented PAD;
- revision of 1 criterion for documented PAD to: history of lower extremity peripheral artery disease with previous related intervention in a leg.

Protocol VMNHU-003/G introduced the following changes to the exclusion criteria:

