3. STUDY DESIGN

This is a phase III, randomized, double-blind, placebo-controlled, multicenter, 7-month study designed to assess the safety and efficacy of intramuscular injections of VM202 in the calf of diabetic patients with chronic nonhealing foot ulcers and concomitant PAD. Subjects with confirmed PAD and diabetes aged \geq 18 years to \leq 80 years diagnosed with nonhealing foot ulcers will be screened for study eligibility after giving informed consent.

At Screening, standard of care will be initiated that will continue for the duration of the study, as follows:

- Surgical debridement of necrotic tissue or devitalized tissue
- Use of appropriate off-loading when ambulating
- Maintenance of moist wound environment

Three hundred patients (from up to 30 study centers) who meet the eligibility criteria will be randomized in a 2:1 ratio to one of two treatment groups: 200 patients with VM202 (16 mg) plus standard of care or 100 subjects with placebo plus standard of care, respectively. Safety will be monitored throughout the study by an independent Data Safety Monitoring Board (DSMB, Section 8.5).

Patients will receive intramuscular injections in the ipsilateral calf of the affected foot with the target ulcer of either VM202 or placebo on Day 0, Day 14, Day 28, and Day 42 as follows:

Treatment: Days 0, 14, 28, and 42

TREATMENT]	DOSE VM20	FINAL DOSE		
GROUP	DAY 0	DAY 14	DAY 28	DAY 42	VM202 (mg)
VM202	4	4	4	4	16
Placebo	0	0	0	0	0

0 indicates injections of Placebo

VM202 will be delivered in a solution of 0.5 mg VM202 / mL. All subjects will receive sixteen (16) 0.5-mL intramuscular injections of VM202 or placebo at each injection visit.

The schedule of study visits and the clinical parameters that will be measured at the visits are summarized in Table 1 to Table 3 below.

The subjects' target ulcer will be evaluated by photograph, surface area, depth, perimeter and volume measurements. Subjects must have a non-healing ulcer on Day 0 that meets study entry inclusion criterion # 5 and does not meet exclusion criterion #6 to be eligible for study participation. Subjects will continue to come to the clinic once a week for dressing changes and wound assessment until the ulcer has healed or study exit, whichever comes first. Measurement of the target ulcer will be performed at each follow-up visit until complete wound closure or study exit.

Further details on the study procedures and conduct are provided in the protocol.

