6. SAMPLE SIZE CALCULATION

Based on prior VM202 studies, the percentage of subjects achieving complete wound closure by the 4-month follow-up (i.e., 4-month responder rate) for VM202 (treatment arm) is assumed to range from 50% to 60%, and that for the placebo group is assumed to range from 20% to 30%. Table 4 below summarizes the statistical power for a sample size of 200 VM202 and 100 placebo subjects based on Fisher's exact test with a two-sided significance level of 0.05 for the statistical hypothesis specified in Section 4.1.

Table 4 Statistical power by estimated responder rates for Treatment (pt) and Control (pc) arms

Pt	рc	Statistical Power
0.50	0.20	>.999
0.50	0.25	0.985
0.50	0.30	0.898
0.55	0.20	>.999
0.55	0.25	0.999
0.55	0.30	0.982
0.60	0.20	>.999
0.60	0.25	>.999
0.60	0.30	0.998

Except for the assumption of $p_t = 0.50$ and $p_c = 0.30$, the statistical power for all assumptions of p_t and p_c is > 0.95. For the assumption of $p_t = 0.50$ and $p_c = 0.30$, the statistical power is about 90%.

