8.6.2. Missing / Unknown Values of Covariates

For categorical covariates, the missing / unknown values will be combined with the category with the most subjects if the missing / unknown rate is $\leq 2\%$ of the pooled data and will be classified into a separate category if the missing / unknown rate is $\geq 2\%$ of the pooled data. If the covariate is also used as a subgrouping variable, the imputed values of the subgrouping variable will not be used for subgroup categorization.

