10. INTERIM ANALYSIS

Due to the early stopping of the study, the protocol-specified interim analysis will not be conducted.

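### With 44 subjects enrolled, the supportive covariate-adjusted logistic model names no sparse-data method; ordinary maximum likelihood would overstate the treatment log odds ratio by about 15-19% on average and occasionally give no estimate.

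*SAP*

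**What the plan says.** - **Adjusted model (SAP 9.4.3).** "The logistic regression model with treatment and all covariates listed in Section 4.5 will be used to obtain the 2-sided 95% confidence intervals" for the adjusted treatment effect on the primary endpoint. Neither the estimator nor the interval type is named. SAP 4.5 lists wound location (collapsed to weight-bearing or not), age and baseline wound area (each split at the median): three two-level factors.
- **Unadjusted model (SAP 9.4.1.2.1).** Treatment is the only term. "The odds ratio and corresponding 2-sided 95% Wald confidence interval will be provided". There is no provision for a fit that does not converge.
- **Sample.** SAP 1: "There were 7 subjects enrolled under protocol version C, 5 enrolled under version E, 16 enrolled under version F, and 16 enrolled under version G", with none under versions D, H or I. SAP 10: "Due to the early stopping of the study, the protocol-specified interim analysis will not be conducted". The design was for 300 subjects, who "will be randomized in a 2:1 ratio to one of two treatment groups".
- **Assumed rates (SAP 6).** The 4-month responder rate for VM202 "is assumed to range from 50% to 60%, and that for the placebo group is assumed to range from 20% to 30" per cent.
- **Missing covariate values (SAP 8.6.2).** Values are merged into the most frequent category up to a 2% missing rate. Above that they form their own level: the data "will be classified into a separate category if the missing / unknown rate is" at or over the cut-off.
- **Status.** SAP 8.4 and 9.1 call the sensitivity and covariate-adjusted analyses supportive. The primary analysis (SAP 9.4.1.1) is Fisher's exact test in the ITT population.

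**The concern.** The logistic models were written for 300 subjects and were not revisited after the early stop. Maximum likelihood estimates of a log odds ratio are biased away from zero in small samples, and the bias grows with the number of parameters per event. At 300 subjects it is negligible; at 44 it may not be. With about 15 placebo subjects and a low healing rate, there is also a real chance of no placebo responder, in which case the estimate is infinite and a Wald interval has no meaning.

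At stake is the effect size that the supportive analyses report. In a trial this small, the odds ratios may well be quoted next to the Fisher p-value. An estimate that leans away from the null on average flatters VM202 whenever it works. A fallback chosen after unblinding would be post hoc.

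**Working it through.** **Inputs.** N = 7+5+16+16 = 44 (SAP 1). Responder rates are 50-60% and 20-30% (SAP 6). Allocation is 2:1; the documents do not give the actual split, so 29:15 is assumed. The model has an intercept and four slopes (SAP 4.5, 9.4.3). The covariates are taken as balanced and independent, each with an assumed odds ratio of 1, 2 or 3.

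**1. The plan's own figure.** The documents give no figure for the logistic models. The nearest is SAP Table 4: power 0.898 for 50% v 30% with 200 v 100 subjects. A continuity-corrected normal calculation gives 0.898, and an exact Fisher calculation that doubles the one-sided p-value gives 0.897. The stated rates and planned sample are therefore understood correctly.

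**2. Events at N = 44.**
- Lowest: 29×0.50 + 15×0.20 = 17.5
- At 50% v 25%: 29×0.50 + 15×0.25 = 18.25
- Highest: 29×0.60 + 15×0.30 = 21.9

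Per slope this is 17.5/4 = 4.4 to 21.9/4 = 5.5 responders.

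**3. Bias of the adjusted log odds ratio.** 6,000 simulated trials were run per scenario. Maximum likelihood (ML) is summarised over estimable fits only, which favours it. Bias is measured against the conditional (covariate-adjusted) odds ratio, so the usual gap between adjusted and unadjusted odds ratios is not counted as bias.

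| Scenario | True OR | ML geometric mean | ML log-OR bias | Firth median OR |
|---|---|---|---|---|
| 50% v 25%, covariate OR 1, N = 44 | 3.00 | 3.58 | ln 3.58 / ln 3.00 = 1.275/1.099, +16% | 2.90 |
| 50% v 25%, covariate OR 3, N = 44 | 3.69 | 4.70 | +19% | 3.52 |
| 50% v 20%, covariate OR 2, N = 44 | 4.44 | 5.52 | +15% | 4.12 |
| 60% v 30%, covariate OR 2, N = 44 | 3.88 | 4.96 | +18% | 3.80 |
| 50% v 25%, covariate OR 2, N = 300 | 3.27 | 3.34 | +2% | 3.22 |

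Over all scenarios at N = 44 the ML bias is about +15 to +19%. The mean log odds ratio from Firth is within about 0 to +3% of the truth and always finite. In a separate simulation at a true log odds ratio of 1.10, ML averaged 1.28 and Firth 1.11, with root mean squared errors of 0.87 and 0.75. The N = 300 row shows that the reduced sample is the cause.

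**4. Inestimability.** P(no placebo responder among 15) is 0.80^15 = 3.5%, 0.75^15 = 1.3% and 0.70^15 = 0.5%. In the simulations the treatment coefficient was inestimable in 0.4% to 5.0% of trials, mainly for this reason.

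**5. Unadjusted model.** Exact enumeration at 29:15 over estimable outcomes gives geometric means of 2.50, 3.24 and 4.30 for true odds ratios of 2.33, 3.0 and 4.0, about 5-8% on the log scale; across all checks the range is about 3-8%. The zero-responder probabilities of step 4 apply here directly.

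**6. Interval coverage.** Coverage of the 95% Wald interval in the adjusted model was 0.956 to 0.979. The median ratio of upper to lower limit was about 24 (50% v 25%, covariate OR 2).

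**7. The 2% rule.** 1/44 = 2.27%, so one missing value already exceeds the cut-off; at 300 the merge branch covered 0.02×300 = 6 subjects. Fitting the model with a one-subject category makes only that category's coefficient diverge. The treatment log odds ratio and standard error equal those after deleting that subject (1.0457, SE 0.749, both ways). Over 6,000 trials the mean treatment log odds ratio was 1.399 with such a category and 1.394 without, and the inestimable share 1.6% v 1.4%.

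**The case against.** **Consequence.** No trial conclusion rests on these models. Fisher's test and the difference in responder rates can still be reported with zero placebo responders, and SAP 9.4.2 adds Cochran-Mantel-Haenszel tests adjusted for each of the same three variables. This stands and limits the weight of the point.

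**Bias against imprecision.** The bias of 1.28 - 1.10 = 0.18 against a root mean squared error of 0.87 is 0.18²/0.87² = 4% of the mean squared error, and coverage is adequate. This also stands: the defect lies in the point estimate and in estimability. Firth nevertheless lowers the total error as well (0.75 v 0.87), so nothing is traded away.

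**Estimator.** Ordinary maximum likelihood is inferred from silence. It is the natural reading of a logistic regression in SAS (SAP 9.1) with a Wald interval named for the companion model. If another method was intended, the SAP should say so.

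**A stronger reading to resist.** A reader might infer that the missing-covariate rule itself inflates the treatment odds ratio or makes it inestimable. Step 7 shows that it does neither: in effect it drops one subject from the adjusted ITT estimate. Nor is it likely to be triggered. Age and ulcer area are eligibility items, area is re-measured before dosing, wound location has already been reviewed, and no missing covariate values are reported. A fixed minimum count such as five subjects would be no better: the documents give no basis for it, and it would assign up to 4/44 = 9% of unknown values to a largest category that is nearly arbitrary for a median split.

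**Conclusion.** The point holds for the adjusted model in SAP 9.4.3. With an effect present, the expected overstatement is about 15-19% on the log scale, roughly 3.6 for a true 3.0. This is an average tendency and says nothing certain about the one realised estimate. An inestimable treatment odds ratio is uncommon, at about 0.4-5%. For the unadjusted model in 9.4.1.2.1 the bias alone (about 3-8%) would hardly justify a change; the missing fallback for zero placebo responders does.

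The figures rest on an ITT population of 44, a 29:15 split, the SAP's responder rates, balanced independent covariates with odds ratios of 1 to 3, and maximum likelihood as the default. The documents do not support reading the Wald intervals as too narrow, or the primary result as affected. This is a cheap improvement to supportive analyses: consider. The one-subject category under SAP 8.6.2 is a separate, minor note.

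**What to change.** In SAP 9.4.3, name Firth penalised-likelihood logistic regression with profile penalised-likelihood 95% confidence intervals. For consistency, use the same method in 9.4.1.2.1 in place of the Wald interval, so that both odds ratios exist even with no placebo responder. Make the change before unblinding.

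The cost is one option in the logistic procedure and one sentence in each section. The downside is mild shrinkage of the estimate. No data collection or primary analysis changes.

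For SAP 8.6.2, it is enough to acknowledge that at N = 44 any missing covariate value forms its own category, and to report any subject who thereby stops contributing to the adjusted treatment estimate. No new numerical threshold is needed.

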9.4.4. Other Efficacy Endpoints

All the exploratory efficacy analyses will be based on the available data in the ITT population.

9.4.4.1. Time to complete wound closure of foot ulcer

The log-rank test will be used to compare the distributions of the time to complete wound closure (event) between the treatment groups. Kaplan-Meier estimates of the survival function for each treatment group will be graphically displayed. Kaplan-Meier estimates of quartiles

Helixmith Co., Ltd.

Page 26 of 31

¹ Gail, MH, and Simon, R., Testing for qualitative interactions between treatment effects and patient subsets. Biometrics, 1985;41: 361-372.

(25th, median, and 75th percentiles) with 2-sided 95% confidence interval will be calculated if estimable.

The log-rank test and Kaplan-Meier methods above will be performed for this endpoint for each subgroup identified in Section 7.5 meeting the minimum group size requirement. Differences between the time-to-event distributions of the treatment groups will be compared adjusting for the subgrouping variable using the log-rank test with the subgrouping variable added as a stratification factor in the modeling.

9.4.4.2. Proportion of subjects with a wound closure by 7 months.

The proportion of subjects with wound closure by the 7-month follow-up will be calculated for each treatment group. The 95% confidence intervals of the proportion will be provided based on the binomial distribution and the exact 95% confidence intervals of the proportion difference will also be obtained. Fisher's exact test will be used to compare the proportions between two treatment groups.

The subgroup analyses described in Section 9.4.2 will also be performed for this exploratory endpoint.

9.4.4.3. Percent change in wound volume at 2, 2.5, 3, 4, and 7 months

The percent change in wound volume at 2, 2.5, 3, 4, and 7 months from baseline will be summarized for each treatment group and compared between the treatment groups using a linear mixed-effects model for repeated measures². The model will include treatment, visit, and treatment-by-visit interaction as the main fixed effects, and baseline wound volume as a covariate using an unstructured variance-covariance matrix. The point estimates for the least-squares mean of the treatment difference (VM202 – Placebo) at each visit and the corresponding 95% confidence interval and p-value will be summarized. Other variance-covariance structures may be substituted if convergence problems arise using corrected Akaike's information criterion (AICC) to pick from among the following structures: compound symmetry (CS), autoregressive ("AR(1)"), variance components (VC), and Toeplitz (TOEP).

The repeated measures analysis above will be performed for this endpoint for each subgroup identified in Section 7.5 meeting the minimum group size requirement. Differences between treatment groups will be compared adjusting for the subgrouping variable using the repeated measures with the subgrouping variable added as a fixed effect in the modeling.

9.4.4.4. Percent change in wound perimeter, area and depth at 2, 2.5, 3, 4, and 7 months

The analyses on the percent change in wound perimeter, area and depth at 2, 2.5, 3, 4, and 7 months from baseline will be based on statistical methods described in Section 9.4.4.3 with the corresponding baseline wound measurement as the covariate.

_

Vonesh, EF and Chinchilli, VM (1996), Linear and Nonlinear Models for the Analysis of Repeated Measurements, New York: Marcel-Dekker.

9.4.4.5. Proportion of subjects with formation of new ulcers on the target foot by 2, 2.5, 3, 4, and 7 months

The proportion of subjects with new ulcers formed by the 2-, 2.5-, 3-, 4-, and 7- month follow-up visits will be calculated for each treatment group. The 95% confidence intervals of the proportion will be provided based on the binomial distribution and the exact 95% confidence intervals of the proportion difference will also be obtained. Fisher's exact test will be used to compare the proportion between the treatment groups at each time point.

The subgroup analyses described in Section 9.4.2 will be performed for these exploratory endpoints.

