9. STATISTICAL METHODS

9.1. General Principles of Data Analyses

The primary analyses of the efficacy endpoints (Sections 9.4.1.1, 9.4.4) will be based on the ITT population. Additional sensitivity analyses for the primary efficacy endpoint, utilizing other populations and/or different ways of handling missing data, will be performed to further assess the effects of the treatment (Section 9.4.1.2). Supportive subgroup and covariate-adjusted analyses of the primary efficacy endpoint in the ITT population are described in Sections 9.4.2 and 9.4.3, respectively. Analyses of the safety outcomes (Section 9.5) will be based on the safety population.

The statistical analyses will be reported using summary tables, figures and listings. Continuous variables will be summarized with means, standard deviations, medians, minimums, maximums, and number of non-missing observations for each treatment group. Other selected percentiles, such as the 25th percentile and 75th percentile, may be presented for parameters that are not normally distributed or are suspected of exhibiting that tendency. Categorical variables will be summarized by counts and the percentage of subjects in corresponding categories. All data collected, including for subjects screened but not randomized, will be included in data listings.

All inferential statistical analyses will be performed with a two-sided confidence level of 95% or a two-sided significance level of 0.05.

All analyses and tabulations will be performed using SAS® Version 9.3 or higher on a PC platform.

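### The fallback covariance structures for percent change in wound size all assume equal variance at every visit, so per-visit intervals can be miscalibrated if the fallback is used and the variances differ

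*SAP*

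**What the plan says.** SAP 9.4.4.3 covers "The percent change in wound volume at 2, 2.5, 3, 4, and 7 months from baseline". The repeated-measures model has treatment, visit and their interaction as fixed effects, and "baseline wound volume as a covariate using an unstructured variance-covariance matrix". A least-squares mean treatment difference, 95% confidence interval and p-value are reported at each visit.

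The fallback clause reads "Other variance-covariance structures may be substituted if convergence problems arise". AICC is the selection rule, and four candidates are named: compound symmetry (CS), autoregressive AR(1), variance components (VC) and Toeplitz (TOEP). The section mentions no heterogeneous-variance version and no empirical standard error.

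The model is reused in two ways. SAP 9.4.4.4 applies it to perimeter, area and depth. SAP 9.4.4.3 adds "The repeated measures analysis above will be performed for this endpoint for each subgroup identified in Section 7.5", provided the minimum group size is met, which SAP 9.4.2 sets at 10% of subjects.

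SAP 9.1 fixes the software, and so the meaning of the structure names: "All analyses and tabulations will be performed using SAS® Version 9.3 or higher on a PC platform".

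**The concern.** The planned unstructured matrix gives each visit its own variance. The fallback removes that for every visit at once, whichever candidate AICC prefers. AICC ranks the four against one another, but none of them can represent a spread that changes between Day 60 and Day 210.

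This matters because the output is a separate interval and p-value at each visit. A common variance is roughly right for an average visit and wrong at the extremes. If late visits are the more variable, the Day 210 interval is too short and its p-value too small. If they are the less variable, the early visits have that problem. VC has a further defect: it treats a subject's five measurements as independent.

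**Working it through.** **Inputs from the documents**
- Visits in the model: Days 60, 74, 90, 120 and 210 (SAP 4.2 and 9.4.4.3).
- Unstructured parameters: 5 variances + 5×4/2 = 10 covariances, so 15.
- Subjects enrolled: 7 + 5 + 16 + 16 = 44 (SAP 1). At 2:1 this is about 29 and 15; the exact split is assumed. A median split gives about 22 per subgroup.
- Wound size is measured until closure (SAP 5.3.2).
- SD of percent change by visit: not given. All SD patterns below are assumptions.

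The plan states no figure on this point, so there is none to reproduce.

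**Step 1. What the four structures allow.** Writing out the 5×5 matrices with variance s² gives the same diagonal each time: s², s², s², s², s². This holds for CS, AR(1), TOEP, and VC as a repeated structure with no grouping option.

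**Step 2. Effect on one interval.** With complete data and a fitted common variance close to the mean of the visit variances:
- pooled SD = √(mean of SD²)
- standard-error ratio at visit t = pooled SD / SD at visit t
- coverage = 2Φ(1.96 × ratio) − 1

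For SDs 30, 32, 35, 40, 50: the mean variance is 7249/5 = 1449.8 and the pooled SD 38.1. At Day 210 the ratio is 38.1/50 = 0.76 and coverage about 86%.

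For SDs 30, 35, 40, 50, 70: the mean variance is 11125/5 = 2225 and the pooled SD 47.2. At Day 210 the ratio is 47.2/70 = 0.67 and coverage about 81%. At Day 60 the ratio is 47.2/30 = 1.57, so that interval is 57% too wide.

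The same formula over evenly stepped SDs, including no change and a fall:

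| SD, first to last visit | Coverage, Day 60 | Coverage, Day 210 |
|---|---|---|
| equal | 0.950 | 0.950 |
| 1 to 1.5 | 0.987 | 0.901 |
| 1 to 2 | 0.997 | 0.869 |
| 1 to 3 | 1.000 | 0.834 |
| 2 to 1 | 0.869 | 0.997 |

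**Step 3. Simulation with AICC selection.** Settings: 29 versus 15 subjects, complete normal data, correlation 0.7 to the power of the visit lag (assumed), no baseline covariate, 400 runs. All four structures were fitted by REML and AICC chose one, AR(1) in 358 to 376 of the 400 runs.

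| SD pattern | Fallback, Day 60 | Fallback, Day 210 | Unstructured, range over visits |
|---|---|---|---|
| equal | 0.955 | 0.958 | 0.950–0.970 |
| 1 to 2 | 0.998 | 0.875 | 0.922–0.958 |
| 1 to 3 | 1.000 | 0.808 | 0.925–0.940 |
| 2 to 1 | 0.912 | 0.995 | 0.932–0.958 |

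**Step 4. Do heterogeneous structures help?** Same set-up, 200 runs, Monte Carlo error about 1.5 to 2.5 points.
- SDs 30 to 70: the listed fallback covered 1.00 at Day 60 and 0.865 at Day 210. CSH and ARH(1) each gave 0.97 and 0.955.
- SDs 30 to 50: the listed fallback gave 0.88 at Day 210; CSH and ARH(1) gave 0.95.
- Equal SDs: CSH gave 0.93–0.95 and ARH(1) 0.92–0.955 across visits, so little is lost when the variances are equal.

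TOEPH and a sandwich standard error were not run.

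**Step 5. Can the fallback be reached?** The 10% rule admits a subgroup of 5 (0.10 × 44 = 4.4, rounded up). Five subjects in two arms leave 5 − 2 = 3 residual degrees of freedom per visit, so an unstructured 5×5 matrix would be singular. The documents do not say that any subgroup is this small.

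**The case against.** The best reply is that the analysis planned is the unstructured one, which is free of this problem, and that the substitution is optional and conditional. A reader might infer from 15 covariance parameters in 44 subjects that convergence will probably fail. The documents do not support that: none reports a convergence problem, and a parameter count does not show one. In trial fits under assumed inputs (the SD pattern from 30 to 70, lag correlation 0.7 or 0.9, 40% dropout by the last visit), the unstructured model converged to a valid matrix in 20 of 20 runs at each correlation, both at 29 versus 15 and at 15 versus 7. Those fits used SciPy rather than SAS and normal data, so they are reassuring but not conclusive.

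A reader might also infer that percent change spreads over time, making late intervals too narrow. The documents do not settle the direction. Percent change is bounded at −100%, and measurement stops at closure. Suppose a proportion p of wounds is closed and counted as −100%, and the rest have mean −30 and SD 50 (assumed). The overall variance is then (1 − p) × 50² + p(1 − p) × 70², giving an SD of 53 at 20% closed, 47 at 60% and 36 at 80%. If closed wounds instead drop out of the data, the pattern differs again.

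A third tempting reading is that a fallback necessarily gives wrong intervals. It does not: with equal variances coverage is nominal.

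All three replies stand as limits on the point. None removes the structural fact that the listed candidates cannot accommodate unequal variances.

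**Conclusion.** The point holds as a conditional weakness in a stated rule. Miscalibration requires three things together: a fallback is used, the visit variances differ materially, and model-based standard errors are kept. Where all three hold, the error runs both ways. Day 210 coverage is about 86% or 81% under the two assumed rising patterns. It is conservative under a falling one, where the shortfall moves to the early visits. These sizes rest wholly on assumed SDs, and the closed form also on complete data.

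The consequence is limited. SAP 8.4 classes these endpoints as exploratory, and the primary Fisher's exact test in SAP 9.4.1.1 does not use this model. It is a cheap improvement, not a threat to the trial's main conclusion.

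**What to change.** In SAP 9.4.4.3, and so by reference in 9.4.4.4:
- Add heterogeneous-variance structures to the fallback in a fixed order. Put CSH first, because it does not depend on visit spacing; the gaps here are 14, 16, 30 and 90 days, and ARH(1) and TOEPH treat them as equal steps. ARH(1) or TOEPH would follow.
- Alternatively, require an empirical (sandwich) standard error whenever an equal-variance structure is used.
- Drop VC, which ignores within-subject correlation.
- State that subgroups too small for any of these models are summarised descriptively.

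The cost is SAP wording and SAS options. The heterogeneous versions use four more variance parameters than their equal-variance counterparts (five variances instead of one), which the smallest subgroups may not support. A sandwich standard error can itself be unreliable with few subjects. The change should be made before unblinding; if that has passed, the heterogeneous fit should be reported as a labelled post hoc sensitivity analysis.
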